balance the number of subjects while maintaining proof of acceptable
performance. The PG will be met if the upper confidence limit from the
95% two-sided Clopper-Pearson confidence interval on the primary
outcome of hernia recurrence rate within three months is less than 8.6%.
The null and alternative hypotheses are given below:
H ₀ : three-month recurrence rate \geq 8.6% versus
H ₁ : three-month recurrence rate < 8.6%.
A binomial test for proportion with a one-sided alpha of 0.025 will be used
to test the hypothesis. A total of enrollment of approximately 110 leaves
100 evaluable subjects assuming a 9% attrition within 3 months. With 100
evaluable subjects the power to reject the null hypothesis is over 90%
assuming an event rate of 1.0%. With 100 evaluable subjects if 3 or less
recurrences (3 %) are observed, the PG will be met.
Continuous variables will be summarized using means, standard
deviations, quartiles, minimum, maximum values and 95% confidence
intervals as appropriate. Categorical variables will be summarized using
counts, percentages and 95% confidence intervals as appropriate.

AFFIX (MaxTa Clinical Invest				
MDT23014	Revision	3.0	Page 20 of 97	Medtronic

4. Introduction

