 - Change in subject Quality of life (QoL), as measured through the administration of the Hernia Quality of Life Survey (HerQLes) questionnaire, evaluated at screening and compared to the following timepoints:
 - o at Month 1
 - o at Month 3
 - o at Month 12

6. Study Design

This prospective, post-market, multicenter, nonrandomized, single-arm, interventional clinical study will evaluate the performance and safety of the MaxTack[™] Motorized Fixation Device when used for fixation in minimally invasive ventral hernia repair procedures.

The study is expected to be conducted at approximately 10 study sites located in the United States (US). However, additional sites in other regions may be added as needed to meet study objectives. Approximately 110 subjects will be enrolled in the study using the MaxTack[™] Motorized Fixation Device. Enrolled subjects will be subjects who have signed an informed consent form, who meet all eligibility criteria and at least one MaxTack[™] tack is utilized for fixation. Study subjects will be evaluated at Screening (-60-0 days preoperative), Operative, Discharge, Month 1 (30-51 days postoperative), Month 3 (90-120 days postoperative), and Month 12 (365-410 days postoperative) visits.

Measures to control bias:

Enrollment parameters are included in the study to avoid introduction of bias to the study results due to disproportionate enrollment. Enrollment shall not exceed 25 subjects per site (this is 25% of the minimum

AFFIX (MaxTa Clinical Invest				
MDT23014	Revision	3.0	Page 24 of 97	Medtronic

number of evaluable subjects needed [100]). Enrollment will be competitive across study sites. The perstudy site enrollment cap may be increased upon sponsor approval. At any time, the study sponsor may place an enrollment hold on individual sites for reasons relating to data quality, overall performance, concerns with Principal Investigator (PI) oversight, or other reasons not specified within the Clinical Investigative Plan (CIP).

All investigators will be required to provide financial disclosure (FD). Physicians will not be able to participate if they have any significant conflict of interest that cannot be mitigated in this study.

Physicians performing procedures will be qualified surgeons experienced with hernia repair procedures.

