10.3 Scheduled Follow-up Visit Windows

Data analyses for follow-up visit data will be conducted regardless of whether the visit occurs within the window. A late visit is preferred over an early or missed visit. Should a subject miss a visit or the visit falls outside the prespecified window, a study deviation must be reported, and the original follow-up schedule must be maintained for subsequent visits.

Follow-up visit windows are listed in Table 4 below and are based on the Operative day.

Study Follow-up	Window (days from Operative Day)					
Visit	Window Start / Target	Window End				
Screening	-60	0				
Operative	0	0				
Discharge	0	n/a				
Month 1	30	51				
Month 3	90	120				
Month 12	365	410				

Table 4: Subject Follow-up Visit Windows

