10.14.5 Lost to Follow-up (LTFU)

Subject lost to follow-up (LTFU) should be avoided as much as possible, and investigators are urged to do their best to maintain subject follow-up compliance. The site will make every attempt to contact subjects that are noncompliant with study follow-up visits. A subject is considered to be lost to follow-up if the following attempts to contact the subject are unsuccessful:

- Three (3) phone calls should be made to the subject at various times and at least one day apart.
 Each attempt should be clearly documented in the source documents and the response or lack thereof should be captured.
- If there is no response to the phone calls, then an official, certified letter should be written and sent to the subject. A copy of the letter and return or delivery receipts should be retained in the subject's source document.

In case a subject can no longer be found, the monitor shall check the appropriateness of the site's attempts to contact the subject.

The sponsor must be notified, and the study exit eCRF must be completed. The monitor shall check the appropriateness of the site's attempts to contact the subject.

The subject will not be considered lost to follow-up until the end of the study (Month 12 follow-up visit). When subjects are considered lost to follow-up the investigator will make efforts to confirm the vital status/health status of the subject, as described in the informed consent. Lost to Follow-up subjects will not be replaced. At the end of the study, the study exit eCRF will be completed with a status of Lost to Follow-up.

AFFIX (MaxTack [™] Motorized Fixation Device) Clinical Investigation Plan				
MDT23014	Revision	3.0	Page 47 of 97	Medtronic

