14.5 Secondary Objective(s)

The secondary objective of this study is to evaluate the performance and safety of the MaxTack[™] Motorized Fixation Device when used for fixation in minimally invasive ventral hernia repair procedures within 12 months post procedure.

See Section 5.2.2 for a full list of secondary endpoints.

Where applicable, descriptive statistics and 95% confidence intervals will be used to summarize secondary study endpoints. Continuous variables are presented as means, standard deviations (SD), medians, first and third quartiles, and minimum/maximum and categorical variables as counts and percentages. A statistical summary of secondary endpoints will be based on data from the full analysis set for subjects, with non-missing data for each secondary endpoint. Recurrence endpoints will be based on a previous recurrence or evaluable data at the time point.

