14.7 Handling of Missing Data

The primary analysis will be based on observed data from all subjects enrolled and receiving study devices (full analysis set) with no imputation for missing data. A sensitivity analysis with all possible outcome values for any missing data will be run on the primary endpoint analysis to assess the robustness of the study results. All practical monitoring and follow-up steps will be taken to ensure complete and accurate data collection.

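### Does the Section 14.5 rule for recurrence endpoints overstate 12-month recurrence enough to need a change?

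*Protocol*

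**What the plan says.** Section 14.5 summarises secondary endpoints on the full analysis set, for subjects "with non-missing data for each secondary endpoint", and reports "categorical variables as counts and percentages". For recurrence it adds that "Recurrence endpoints will be based on a previous recurrence or evaluable data at the time point". A subject therefore counts at Month 12 in one of two ways: a recurrence is already on record, or Month 12 status is evaluable.

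Four other places bear on the point.
- The Synopsis plans for "100 evaluable subjects assuming a 9% attrition within 3 months". No attrition figure is given for Month 12.
- Section 6 schedules the last two visits as "Month 3 (90-120 days postoperative), and Month 12 (365-410 days postoperative) visits", so nothing is scheduled between day 120 and day 365. Section 10.3 adds: "Data analyses for follow-up visit data will be conducted regardless of whether the visit occurs within the window".
- Section 10.14.5: "Lost to Follow-up subjects will not be replaced".
- Section 14.7: "A sensitivity analysis with all possible outcome values for any missing data will be run on the primary endpoint analysis". The 12-month rate is not named there.

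**The concern.** Among subjects who leave, inclusion depends on the outcome. A subject with a recurrence at Month 1 or 3 who is then lost sits in both numerator and denominator. A subject examined and found recurrence-free at Months 1 and 3 who is then lost meets neither condition and disappears. If leaving has nothing to do with recurrence, non-recurrers are thinned out more than recurrers and the proportion drifts upward.

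The 12-month rate is the longest performance result in the trial, and Section 6.1 gives full absorption of the tacks by 12 months as the reason for following subjects that long. More subjects may be missing at Month 12 than at Month 3, and the one sensitivity analysis for missing outcomes is attached to the Month 3 endpoint. If the bias were material, the long-term figure would mislead and the protocol would name no check on it.

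**Working it through.** **The plan's own figures.** The protocol states no 12-month figure. Its primary figures reproduce: the Clopper-Pearson upper limit is 8.52% for 3/100 and 9.93% for 4/100, against the goal of 8.6%; power at a 1.0% rate is 98.2%; and 100/0.91 = 110. None of these depends on how the 12-month rate is computed.

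**Direction.** Let p be the true 12-month recurrence and L the loss by Month 12, unrelated to recurrence. The rule retains (1 - p)(1 - L) of the cohort as recurrence-free and at least p(1 - L) as recurrent. The reported proportion is therefore at least p. It equals p only if nobody is lost after a recorded recurrence.

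**Inputs.** Visits at days 30, 90 and 365 and N = 110 are from the protocol. Constant hazards are assumed. The assumed p is 4% (the plan's 1.0% at 3 months carried forward: 1 - 0.99^(365/90) = 4.0%) or 10%. The assumed L is 9%, 15% or 20%, with an extreme of 32% (the plan's 9% at 3 months carried forward: 1 - 0.91^(365/90) = 31.8%).

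**Formula.** S(t) = (1 - p)^(t/365) and G(t) = (1 - L)^(t/365). With detection only at visits, E is the sum over visits v of [S(previous) - S(v)] × G(v), and the rule's expected value is E / [E + S(365)G(365)].

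**Worked case, p = 4%, L = 20%** (unrounded values carried).
- S(30) = 0.99665 and S(90) = 0.98998; G(30) = 0.98183 and G(90) = 0.94646.
- E = 0.00329 + 0.00631 + 0.02399 = 0.03359.
- S(365)G(365) = 0.96 × 0.80 = 0.768.
- Rule = 0.03359/0.80159 = 4.19%.
- Extra recurrers kept: 110 × (0.03359 - 0.04 × 0.80) = 0.17 subjects.

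**All cases.**

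| Loss by Month 12 | True 4% | True 10% |
|---|---|---|
| 9% | 4.08% | 10.18% |
| 15% | 4.13% | 10.32% |
| 20% | 4.19% | 10.45% |
| 32% | 4.35% | 10.83% |

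For 9% to 20% loss the extra recurrers run from 110 × (0.03712 - 0.0364) = 0.08 (true 4%, 9% loss) to 110 × (0.08406 - 0.08) = 0.45 (true 10%, 20% loss). If the planned 9% are lost by Month 3 and nobody later, the results are 4.02% and 10.05%.

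**Other timing of detection.** If half of recurrences are found promptly between visits, the bias is 0.1 to 0.8 points at 9% to 20% loss. If all are captured as they occur, a true 10% becomes 10.44% to 11.09%. The bound, with every recurrence preceding every loss, is p/[p + (1 - p)(1 - L)]. At 20% loss this is 0.10/(0.10 + 0.72) = 12.20% for a true 10%.

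**Yardstick.** One subject is 1/110 = 0.9 points. With about 100 subjects the sampling standard deviation is √(0.04 × 0.96/100) = 2.0 points, or √(0.10 × 0.90/100) = 3.0 points. At 20% loss (88 subjects) and a true 10% it is 3.2 points, still above the 2.2-point bound.

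**Would a life table on nominal visits do better?** With loss unrelated to recurrence and detection only at visits, it returns exactly 4.00% and 10.00%. Now suppose lost subjects have twice the later risk: true 4%, of which 1% falls by Month 3, and a share l of those recurrence-free at Month 3 is lost afterwards. Subjects who stay have later risk q = 0.03/[0.99(1 + l)].
- l = 9%: q = 2.78%. The rule gives (0.01 + 0.9009q)/(0.01 + 0.9009) = 3.85%; the life table gives 1 - 0.99(1 - q) = 3.75%.
- l = 20%: q = 2.53%. The rule gives 3.74% and the life table 3.50%.

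Both fall short of 4%, and the life table falls further short.

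**Missing-outcome range, by example.** Take 4 recurrences and 16 recurrence-free losses among 110. The rule gives 4/94 = 4.3%. If none of the 16 recurred it is 4/110 = 3.6%; if all did it is 20/110 = 18.2%. The inputs are the event count, the denominator and the size of the full analysis set.

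**The case for a change.** The strongest case for a change is the range, not the bias. A reported 4.3% that could lie anywhere from 3.6% to 18.2% deserves a stated check. Section 7.1 puts significant tack absorption at three to five months, inside the unvisited interval, and the recurrence claim in Section 6.1 is not limited to Month 3. The counting rule is written into the protocol, not left open. Section 10.14.6 promises use of all data through exit, yet the 12-month proportion ignores the negative examinations of subjects who later leave. Extending an analysis already planned for Month 3 would cost a sentence.

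The direction of the bias and the width of the range both stand. They do not show that the protocol fixes anything badly. Under the rule, anyone in the full analysis set but outside the 12-month denominator has no recorded recurrence and no evaluable Month 12 status. The set size minus the denominator is therefore the number of unknown outcomes, and the range follows from it. Section 14.1 adds a CONSORT diagram and a summary of visit compliance. The early negative examinations are used in the 1-month and 3-month recurrence endpoints. Section 14 describes itself as high level and leaves detail to the SAP, which is the usual home for a supportive analysis of a descriptive secondary endpoint.

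The 32% loss is also an extrapolation that the follow-up provisions are meant to prevent. Subjects are not declared lost until Month 12 (Section 10.14.5), those withdrawing should be offered record review (Section 10.14.4), recurrence status may be assessed remotely with approval (Section 10.9), and late visits are analysed (Section 10.3).

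**Conclusion.** No change follows. The asymmetry is real. If loss is unrelated to recurrence, detection is at the scheduled visits, hazards are constant and 80% to 91% of subjects are retained, it adds about 0.1 to 0.5 points to a true rate of 4% to 10%. That is under half a subject and well inside sampling error. Faster detection or heavier loss raises it, but even the bounding case at 20% loss stays below one sampling standard deviation. If lost subjects recur more often, the sign can reverse.

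The endpoint has no performance goal and no test (Section 14.8), the primary result is untouched, and under unrelated loss the error counts against the device. Keeping early recurrers is the right half of the rule, and the obvious replacement trades one assumption about loss for another without a dependable gain. Analysts can give the missing-outcome range for Month 12 in the SAP or the report from counts that will be available anyway; the protocol need not be amended for that. All 12-month loss and recurrence rates here are assumptions.

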14.6 Sample Size Determination

The sample size was determined using PASS 2024 v24.0.2. A total of 100 evaluable subjects is estimated to provide over 90% of power, with a one-sided alpha of 0.025, assuming a 3-month hernial clinical recurrence rate of 1.0%, to meet the performance goal of 8.6% (i.e. the upper 95% confidence limit lower

¹ Notes: References 13-22. For Colak et. al. 2015, Zanella et. al. 2019, and Caruso et. al. 2017 an exponentially distributed survival curve was assumed and the interpolated number of events at 3 months was calculated and rounded to the nearest whole number. For Christoffersen. et. al. 2014, the rate at 3 months was estimated using Kaplan-Meier curve. For Harslof et. al. 2018 0% (1M) and 5% (6M and 12M) used 6 month rate of 1 out of 20.

	AFFIX (MaxTack [™] Motorized Fixation Device) Clinical Investigation Plan				
MDT23014	Revision	3.0	Page 61 of 97	Medtronic	

than 8.6%). By accounting for a projected attrition rate of 9%, a total of approximately 110 subjects will be enrolled.

14.7 Handling of Missing Data

The primary analysis will be based on observed data from all subjects enrolled and receiving study devices (full analysis set) with no imputation for missing data. A sensitivity analysis with all possible outcome values for any missing data will be run on the primary endpoint analysis to assess the robustness of the study results. All practical monitoring and follow-up steps will be taken to ensure complete and accurate data collection.

14.8 Multiplicity Adjustment

Only one hypothesis test is planned. All secondary endpoints will be summarized using descriptive statistics, and no multiplicity adjustment will be considered.

14.9 Study Site Pooling

The study will be conducted at approximately 10 study sites in the United States (US). However, additional sites in other regions may be added to meet study objectives. There is no a priori provision to exclude any study sites from the analysis. The data from all study sites will be pooled for analysis. To reduce the possibility of atypical results from a study site overly influencing the combined results, enrollment shall not exceed 25 subjects per site (25% of the minimum number of evaluable subjects needed [100]).

14.10 Minimization of Bias

Selection of subjects, treatment of subjects, and evaluation of study data are potential sources of bias. Methods incorporated in the study design to minimize potential bias are noted in Section 6. In summary, potential sources of bias that may be encountered in this study have been considered and minimized by careful study design.

15. Ethics

15.1 Statement(s) of Compliance

This study will comply with international ethical and scientific quality standards, known as good clinical practice (GCP). GCP includes review and approval by an IRB/EC before initiating a study, continuing review of an ongoing study by an IRB/EC and obtaining and documenting a subject's freely informed consent before initiating any study procedures.

The AFFIX study was designed to reflect the GCP principles outlined in ISO 14155:2020 and other clinical requirements outlined below. These include the protection of the rights, safety, and well-being of human subjects, controls to ensure the scientific conduct and credibility of the clinical investigation and the

AFFIX (MaxTa Clinical Invest				
MDT23014	Revision	3.0	Page 62 of 97	Medtronic

definition of responsibilities of the sponsor and investigators. In accordance with ISO 14155:2020, the sponsor shall avoid improper influence on, or inducement of, the subject, monitor, any investigator(s), or other parties participating in or contributing to the clinical investigation. Investigators will disclose financial conflicts of interest prior to the initiation of the clinical study at the site or during the clinical study for all new investigators added to the site team and investigators who have a change in previously disclosed financial information. All investigators shall avoid improper influence on or inducement of the subject, sponsor, monitor, other investigator(s), or other parties participating in or contributing to the clinical investigation.

The principles of the Declaration of Helsinki (DoH) have been implemented through the Informed Consent (IC) process, IRB/EC approval, study training, clinical trial registration, preclinical testing, risk-benefit assessment, and publication policy. The clinical study shall not begin until the required approval from the IRB/EC and regulatory authorities, if applicable, has been obtained. Any additional requirements imposed by the IRB/EC or regulatory authority shall be followed as appropriate.

Ultimately, all study sites will follow and comply with:

- Principles of DoH (2013)
- 21 CFR Parts:
 - 11 (Electronic Records, Electronic Signatures)
 - 50: (Protection of Human Subjects)
 - 54 (Financial Disclosure by Clinical Investigators)
 - 56 (IRBs)
- The CTA
- The procedures described within this CIP
- Local IRB/EC Requirements
- ISO 14155:2020

All participating sites will make study data available to the regulatory body if the regulatory body deems an onsite inspection necessary. The regulatory body will be able to inspect records at clinical study sites to resolve any uncertainties about whether the study was conducted in accordance with good clinical practice.

The study will be publicly registered prior to in accordance with the 2007 Food and Drug Administration Amendments ACT (FDAAA) and DoH on http://clinicaltrials.gov (PL 110-85, Section 810(a)).

Approval of the CIP and CIP amendments is required from the following groups prior to any study procedures / revised study procedures at a study site:

- Medtronic
- IRB/EC

This study contains the following from ISO 14155:2020:

AFFIX (MaxTac Clinical Investig				
MDT23014	Revision	3.0	Page 63 of 97	Medtronic

- Point of Enrollment: Per ISO 14155:2020, the point of enrollment is the time at which, following recruitment and before any clinical investigation-related procedures are undertaken, a subject signs and dates the informed consent form. In this study, a subject is considered enrolled when it is confirmed: the ICF is obtained, they meet all preoperative inclusion criteria, and they do not meet any preoperative or intraoperative exclusion criteria, and at least one MaxTack[™] tack is used. (See Section 10.6 for Enrollment details). Those subjects who sign the ICF but fail all screening criteria, will not be included in the study. Those subjects who sign the ICF and are considered intraoperative screen failures will not count as an enrollment.
- Adverse Event Collection: Per ISO 14155:2020, all AEs shall be documented. In this study, only AEs related to the MaxTack[™] motorized fixation device, mesh, or study procedure, all events that lead to death, and any non-subject adverse event will be collected. Additionally, adverse events will be collected starting at the time of skin incision. Enrolled subjects will have adverse events collected from skin incision through study exit.
- Unanticipated Serious Adverse Device Effect (USADE): Per ISO 14155:2020, USADEs are defined as, a SADE, which by its nature, incidence, severity, or outcome has not been identified in the current risk assessment. Due to this being a post-market study, USADEs are not applicable, therefore classification of AEs as such is not required.
- Device Labelling: Per ISO 14155:2020, the investigational device, the instructions for use and packaging shall indicate the investigational device is exclusively for use in a clinical investigation. However, since this is a post-market study and the devices are already commercially available, additional investigational labeling is not necessary. All devices will be securely stored within research offices and will not be stored in the operating room with other similar commercially available devices. This controlled storage process ensures that the devices are not mistaken for standard-of-care devices by clinical staff. Furthermore, since the devices are not being utilized outside of the defined study parameters, the risk of misidentification is significantly mitigated, thus justifying the decision to forgo standard investigational labeling.

16. Study Administration

